	Extension Phase: Placebo-treated subjects will be offered the option of receiving treatment with RZL-012 on a single occasion. Dosing will be calculated according to lipoma size (diameter) as determined by ultrasound and will follow the treatment regimen shown in the table above.
Visit Schedule	Subject site visits will be performed ± 1 day from scheduled date for Day 28 and Day 56 visit and ± 2 days from scheduled date for Day 84 visit. All data relevant for the visits should be obtained within 3 days (e.g., blood test results) of visit. Screening Day visit (Day -14 through -1):
	 Following signing of the informed consent - assessment of subject eligibility will include: medical history, physical examination, vital signs, women in fertile age will be asked for pregnancy test, ECG, serology assays (HBV, HCV and HIV), clinical laboratory tests. Ultrasound assessing lipoma/nodules size (diameter) and quality to determine which lipomas/nodules are to be injected with a total dose of up to 240 mg RZL-012. Photography of injection site areas. Clinical laboratory tests will include:
	1. Hematology: Complete blood count (CBC) including White blood cell [WBC] differential values, D-dimer, Fibrinogen and coagulation (International normalized ratio [INR], Partial thromboplastin time [PTT] and Prothrombin time [PT]).
	2. Serum chemistry will include:
	Albumin, Albumin/Globulin Ratio (calculated), Alkaline Phosphatase, ALT, AST, BUN/Creatinine Ratio (calculated), Calcium, Carbon Dioxide, Chloride, Creatinine with GFR Estimated, Globulin (calculated), Glucose, Potassium, Sodium, Total Bilirubin, Total Protein, Urea Nitrogen. In addition, Amylase, Lactate dehydrogenase [LDH], Creatine-kinase MM [CK-MB], Creatine phosphokinase [CPK], Gamma-glutamyl transferase [GGT], Alkaline phosphatase [ALP]) and C-reactive protein [CRP] will be tested.
	 Lipid profile: Total Cholesterol (TC), High Density Lipoprotein (HDL), Low Density Lipoprotein (LDL), Triglycerides (TG) and Fasting glucose. Urinalysis: Protein, Red blood cells (RBC), WBC, Blood, Glucose, Ketone bodies, Bilirubin, Urine specific gravity, pH. Baseline visit (Day 0):
	 Pre-treatment: eligibility confirmation, vital signs, pregnancy test women, Draize score, clinical evaluation of local pain and tenderness to pressure (pain assessment) and lipoma/ nodules size assessment by ultrasound*, photography, QOL questionnaire

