5.1.9. Clinical Laboratory tests

Clinical laboratory tests will be conducted on Screening Day (performed 14 through 1 days prior to baseline) in order to ensure compliance with study inclusion criteria. Additional studies will be conducted on different study visits according to schedule as written below for each set of tests. The maximum total blood volume will be 30 mL per visit. Every out-of-range value will be assessed by a physician and deemed as either clinically significant or clinically not significant. Values that represent a change from baseline in subject's medical status according to the laboratory normal ranges will be adequately documented as an AE as described in Section 8.

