5.1.9.2. Serum Chemistry Analysis

Testing of blood chemistry values will be conducted on Screening Day (performed 14 through 1 days prior to baseline) in order to ensure compliance with study inclusion criteria.

Additional Serum Chemistry testing will be conducted on Day 0 (before injection), $24hr \pm 2hr$ following injection and on study visit Day 1 and Day 28 following injection.

Serum chemistry will include:

Albumin, Albumin/Globulin Ratio (calculated), Alkaline Phosphatase, ALT, AST, BUN/Creatinine Ratio (calculated), Calcium, Carbon Dioxide, Chloride, Creatinine with GFR Estimated, Globulin (calculated), Glucose, Potassium, Sodium, Total Bilirubin, Total Protein, Urea Nitrogen. In addition, Amylase, Lactate dehydrogenase [LDH], Creatine-kinase MM [CK-MB], Creatine phosphokinase [CPK], Gamma-glutamyl transferase [GGT], Alkaline phosphatase [ALP]) and C-reactive protein [CRP] will be tested.

In case a specific subject demonstrates elevated blood levels in one or more of the tested parameters, this subject will be followed up on day 56 to confirm return to normal levels.

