5.2.1. Screening Procedures

All information collected and documented during screening procedures will be reviewed to ensure eligibility in reference to study inclusion and exclusion criteria, and fully documented in subject file.

Screening visit should be performed 14 days ahead and no later than 1 day prior to baseline visit.

Study Screening Day procedures will include the following:

- Informed Consent Section 5.1.1
- Medical History Section 5.1.2
- Concomitant Medication Section 5.1.3
- Physical Examination Section 5.1.4
- Vital signs Measurement –Section 5.1.7
- ECG Section 5.1.10
- Serology -5.1.8
- Clinical laboratory tests Section **Error! Reference source not found.**
- Photography of injected lipomas Section Error! Reference source not found.
- Ultrasound to measure lipoma/nodule dimensions Section 5.1.13

Subjects may be rescreened if they were screened and did not completed their blood and urine tests and not dosed within 14 days. The following procedures will be performed: Clinical Laboratory Tests (hematology, serum chemistry, and urinalysis), vital signs, Draize score and photography.

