Photography of the Injected Sites	At Day 0 visit and at days 28, 56	Day 84
Pain assessment using Comparative Pain Scale	At Days 0, 28, 56	Day 84
QOL assessment	At day 0	Day 84
Serum chemistry and Hematology	At Day 0 and at Days 1, 28	
Urinalysis	At Day 0 and at Days 1, 28	
Lipid Profile	At Day 0 and at Day 1	
AEs assessment	At Days 0, 1, 7, 28, 56	Day 84

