6. DESCRIPTION OF THE OPEN LABEL EXTENSION PHASE OF THE STUDY

At study completion, the randomization codes will be opened. Nineteen (19) Subject who were injected with placebo will be offered to be treated with RZL-012.

At least 4 lipomas/nodules, preferably 6, and no more than 8, will be injected per subject. Dosing will be according to lipoma size, where the total injected dose will not exceed 240mg per patient (48 injections at 5mg/injection).

Dosing will be done according to lipoma size, as described in Table 6:

Table 6: Dosing of RZ-012 in the Open Label Extension Phase

Number of Subjects – Active/Placebo	19/19					
Lipoma/Nodule size – diameter (cm)	1-1.9	2-3.9	4-5.9	6-7.9	8-10	
Total Dose of RZL-012 in the RZL group (mg)	10	20	40	50	60	
Number of Injections	2	4	8	10	12	

The injection with RZL-012 will be done within 30 days of randomization codes opening.

The day that will be set up by the physician for RZL-012 injection will be the baseline visit, Day 0.

On this day, each subject will have the procedures, as described in Section 5.1:

Day 0- Physical exam, Clinical laboratory tests (hematology, chemistry) lipid profile and urinalysis, ECG, injection with RZL-012, concomitant medication, vital signs – before and after the injection, ultrasound measurement of the lipomas*, photography of the lipomas, QOL questionnaire, Draize score – before and after injection, pain score and AEs documentation.

Day 1 – ECG, vital signs, Draize score, clinical laboratory tests including urinalysis and lipid profile, AEs record.

Day 7 – Phone call visit. The study coordinator/nurse will call the subjects to ask about adverse events and general health.

Day $28\pm 2 - ECG$, physical exam, vital signs, clinical laboratory tests, urinalysis, Draize score, ultrasound measurement of the lipomas, photography of the lipomas, pain score and AEs documentation.

Day 56±2 - Physical exam, vital signs, ultrasound measurement of the lipomas, photography of the lipomas, Draize score, pain score and AEs documentation.

Day 84±2 - Ultrasound measurement of the lipomas, photography of the lipomas, QOL questionnaire, Draize score pain score, QOL questionnaire and AEs documentation.

Schedule of events of the open label extension part is presented in Appendix 2.

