APPENDIX I: TRIAL SCHEDULE OF EVENTS

Study Procedure	Double	Double Blind, Randomized, Placebo Controlled			ects (wi	el exter ll be do tudy co	one wit	hin 30					
	Screening Day	Baseline (Treatment)	Visi	Visit Schedule (Days 1 to 84)					Visit Schedule (Day 0 to 84)				
Study Day	Day (-14) through Day (-1)	Day ^a 0	Day 1	Day 7	Day 28	Day 56	Day 84	Day ^d 0	Day 1	Day 7	Day 28	Day 56	Day 84
Signed informed consent	X												
Medical history	Х												
Physical Exam	Х				X	X		Х			X	Х	
Concomitant Medication	X	Х	Х	X	X	X	X	Х	Х	Х	Х	Х	Х
Pregnancy kit test (women) ^b		Х											
Vital signs	X	Pre ^c X post ^c	X		X	X		Pre ^c X post	Х		X	X	
Injection of RZL- 012/Placebo		Х						X					
ECG	Х		Х		Х			Х	Х		Х		
Serology assay	X												
Draize Score		Pre ^c X post ^c	X		X	X	X	Pre ^c X post c	Х		X	X	Х
Ultrasound measure of lipomas	X	Xe			Х	Х	X	х			Х	Х	X
Photography of lipomas	Х	Xe			Х	Х	X	x			X	Х	X
Serum chemistry and hematology	X		x		Х			Х	Х		Х		
Urinalysis	X		Х	1	Х		1	Х	Х	1	Х		

	Double	Double Blind, Randomized, Placebo Controlled							en Lab ects (wi of s		one wit	hin 30	
Study Procedure	Screening Day	Baseline (Treatment)	Visi	t Sched	lule (D	ays 1 t	o 8 4)		Visit Sc	chedule	e (Day	0 to 84)
Study Day	Day (-14) through Day (-1)	Day ^a 0	Day 1	Day 7	Day 28	Day 56	Day 84	Day ^d 0	Day 1	Day 7	Day 28	Day 56	Day 84
Lipid profile	X		Х					Х	Х				
Pain assessment of each lipoma		Х			Х	Х	X	Х			X	Х	Х
QOL questionnaire		Х					Х	Х					Х
AEs assessment		Х	X	Х	X	Х	X	Х	Х	X	Х	Х	Х

a. Day 0 defines the day of RZL-012/placebo injection in the double blinded randomized study

b. At screening visit women will be asked whether they are pregnant, test will be performed at baseline visit before dosing

c. Pre/post - refers to before/after injection, respectively

d. Day 0 defines the day of RZL-012 injection in the open label study

e. In case of screening visit that will be conducted only one day before Baseline, ultrasound and photography at Baseline visit is optional. The ultrasound parameters and photography collected at screening will be used at Baseline visit.

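### Open-label extension: blood and urine safety tests fall on the injection day, and no text requires their results to be seen before a placebo subject's first RZL-012 dose

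*Combined protocol and SAP*

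**What the plan says.** Extension. Section 6 makes the injection day the baseline visit and lists the procedures in one line: "Day 0- Physical exam, Clinical laboratory tests (hematology, chemistry) lipid profile and urinalysis, ECG, injection with RZL-012". The synopsis carries the same list. Table 5 times serum chemistry, hematology and urinalysis as "At Day 0 and at Days 1, 28", and the lipid profile for Day 0 and Day 1. Appendix I has no extension column before Day 0, and its footnote d confirms that "Day 0 defines the day of RZL-012 injection in the open label study". Section 6 allows injection up to 30 days after the codes are opened.

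Blinded phase. Section 5.1.9 says "Clinical laboratory tests will be conducted on Screening Day (performed 14 through 1 days prior to baseline", for the purpose of checking the inclusion criteria. Section 5.2.1 adds that "All information collected and documented during screening procedures will be reviewed to ensure eligibility in reference to study inclusion and exclusion criteria". The synopsis entry for the blinded Day 0 then starts with "Pre-treatment: eligibility confirmation, vital signs, pregnancy test women".

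**The concern.** The two phases use the same drug, the same size-based dosing table and the same 240 mg ceiling, which the synopsis describes as 100% of the NOAEL. In the blinded phase the laboratory results are in hand and reviewed before anyone is injected. In the extension the sample and the injection share a day, and nothing sets the order of result and dose.

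For a placebo subject, extension Day 0 is the first exposure to RZL-012. It is given in one session of up to 48 injections that cannot be undone. A clinically significant abnormality in the Day 0 blood or urine sample can inform the decision to dose only if someone sees it first. The ECG, physical examination and vital signs are not at issue, because they can be read on the spot.

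**Working it through.** No statistical calculation bears on this point. The check has three parts: the dose, the text, and the age of the results on file.

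**1. Dose.** 48 injections × 5 mg = 240 mg, as stated. 240 / 180 = 1.33, which matches the stated 33% above the highest dose previously given to humans.

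**2. Does any text require results before extension dosing?** Five places come close.

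- Section 5.2.5 (Baseline Visit) describes a Day 0 visit that finishes the screening evaluation and confirms eligibility before dosing. Section 6 calls extension Day 0 a baseline visit, and Table 5 sits inside Section 5.2.5, so the sentence can be read to cover the extension. It names neither laboratory results nor the extension, and the extension has no screening to finish. For procedures, Section 6 points to Section 5.1.
- Section 5.1.9: "Every out-of-range value will be assessed by a physician and deemed as either clinically significant or clinically not significant". No time relative to dosing is given.
- Section 5.1.9.2: "Additional Serum Chemistry testing will be conducted on Day 0 (before injection". This orders the sample, not the result, and covers chemistry only.
- The synopsis Visit Schedule asks for visit data, with blood results as its example, within 3 days of the visit. That permits earlier sampling. It does not say before the visit, so results after it would also comply.
- Section 5.2.8 allows unscheduled visits with any Section 5.1 procedure. It does not require one.

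Each permits or implies a check. None requires results first.

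**3. Age of the last routine results at extension dosing.** The last scheduled chemistry, hematology and urinalysis in the blinded phase are at Day 28 (Table 4, Appendix I). The windows are ±2 days for Days 28, 56 and 84 (Section 5.2.6); one synopsis sentence gives ±1 day for Days 28 and 56. Assume the codes open at the subject's own Day 84, with dosing 0 to 30 days later.

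- Nominal: 84 − 28 = 56 days, up to 56 + 30 = 86.
- With ±2 days: (84 − 2) − (28 + 2) = 52 days, up to (86 − 26) + 30 = 90.
- With ±1 day on Day 28: 82 − 29 = 53 days, up to (86 − 27) + 30 = 89.
- Lipid profile, including fasting glucose, last scheduled at Day 1: nominally 84 − 1 = 83 days, up to 83 + 30 = 113.
- Subjects with an elevated value have a Day 56 follow-up: nominally 84 − 56 = 28 days, up to 28 + 30 = 58. The minimum with ±2 days is 82 − 58 = 24.

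In the blinded phase the corresponding tests are at most 14 days old at dosing: 52 / 14 = 3.7.

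Sections 6 and 10.4.1 open the codes at study completion, so subjects who finish early wait longer. The enrollment period is not given, and no upper limit can be set.

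**The case against.** The strongest case is that a sensible investigator already has everything needed. Section 5.2.5 can be read as an eligibility review before dosing, the Day 0 lists put the tests ahead of the injection, and early sampling is allowed. The physician chooses the injection date within 30 days, so nothing forces a dose before results are back. These subjects passed full screening, received only vehicle, and had laboratory tests at Days 1 and 28. This stands as far as it goes. The gap is a missing requirement and not a ban on prior review. Even so, an investigator who injects without waiting departs from no stated rule on laboratory results.

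A second objection concerns the ages above, which matter only if the Day 0 results are not seen before injection. That is correct. Laboratory turnaround is not stated, so a reader might infer that same-day results cannot be back in time. The documents do not support that.

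A third concerns the laboratory signals in Section 1.2.1. A reader might infer that pre-dose review would have averted them. It would not, because both are changes after dosing. Liver enzymes rose in one subject given 20 mg, and this was not seen again at doses up to 180 mg. D-dimer rose 3-fold on average at Day 3 in the 180 mg group and fell by Day 7. They support having a known pre-dose value and no more.

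**Conclusion.** The point holds as a gap in the extension schedule that should be closed. Following the schedule as written can mean an irreversible first dose of up to 240 mg with the latest routine chemistry, hematology and urinalysis seen being at least 52 days old (56 nominally). The blinded phase allows at most 14 days. The size is bounded: at most 19 subjects, and only where Day 0 results are not seen in time. The minimum ages rest on code opening no earlier than the subject's own Day 84 visit and on no unscheduled testing.

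Two stronger conclusions are tempting. One is that dosing without current results would breach the fasting-glucose limit in inclusion criterion 3. Section 6 does not say that the Section 4 criteria are reapplied, so no breach follows. What is missing is any stated laboratory condition for extension dosing. The other is that the trial's main result is weakened. It is not: all of this happens after the codes are opened, and Section 10.4.1 keeps extension efficacy data out of the blinded report.

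**What to change.** In the synopsis, Section 6, Table 5 and Appendix I, take the extension blood and urine tests already listed on Day -14 to -1, once the codes are open and the subject has opted in. This fits within the 30-day window. Alternatively, keep Day 0 sampling only where results are back before injection. In either case, add that the investigator reviews these results for clinically significant abnormalities, using the Section 5.1.9 assessment, before injecting. Leave the ECG, physical examination and vital signs on Day 0.

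Section 5.1.9.2 does not separate the phases. Add an extension-specific sentence there and leave the existing Day 0 chemistry text alone, so that no blinded-phase sample is removed by accident. If the sponsor wants the criterion 3 glucose limit to govern extension dosing, it should be written openly as an added dosing condition.

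The cost is a schedule amendment and at most one short extra visit for each of up to 19 subjects, or none where same-day results are reviewed first. No test is added and no dose changes.

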7. SAFETY CONSIDERATIONS AND GUIDANCE FOR INVESTIGATORS

Adherence to protocol monitoring procedures along with the following safety guidance will aid and promote subject safety.

7.1. STUDY RESTRICTIONS REGARDING CONCOMITANT MEDICATIONS

Subjects may not receive the following medications at least 3 months prior to study entry:

- Chronic treatment with systemic steroids or immunosuppressive drugs.
- Any investigational product other than RZL-012.

Subjects may not receive the following medications at least one week prior to study entry:

• Chronic treatment with Non-Steroidal Anti-Inflammatory Drugs (NSAIDs).

Before dosing, topical analgesic gels such as Lidocaine (e.g., Emla) or Pramoxine may be used to numb the injected site. An ice pack should be applied onto the sites of injection immediately following dosing to help reduce pain.

On Day 1 following injection, application of the antihistamine Benadryl Gel (Diphenhydramine hydrochloride for topical use only), or any other antihistamine generic gel may be initiated prophylactically, according to drug instructions for use, to avoid itching at the injected area. Benadryl Gel or other generic gel should be applied for 7 days or as needed.

7.2. SAFETY MEASUREMENTS

Simple measures may help avoid specific AEs associated with the use of the RZL-012 investigational product. Thus, study subjects must be informed of possible AEs that occurred in animal studies and in previous clinical studies, as introduced in the ICF.

The AEs of RZL-012 vs. placebo will be evaluated for their frequency, severity and duration.

7.3. PREMATURE DISCONTINUATION FROM STUDY

Study may be prematurely discontinued in any of the following cases:

- Subject's request.
- Any life-threatening AE.
- Systemic hypersensitivity reaction.
- Any serious or severe ADR (defined in Section 9.3) clinically evaluated by the PI and/or Sponsor as warranting subject discontinuation.
- Non-compliance: Subject's non-compliance with study procedures, evaluated by PI and/or Sponsor as warranting subject discontinuation.
- Other reasons regarded by PI as warranting subject's discontinuation.
- Premature study termination as described in Section 7.4.

Subjects who discontinue the study prematurely will be queried whether an AE contributed to their decision.

7.4. PREMATURE STUDY TERMINATION

The study will be prematurely terminated in any of the following cases:

- Recurring serious or severe ADR (defined in Section 9.1) clinically evaluated by PI and/or Sponsor as warranting study termination.
- A decision made by Sponsor and/or IRB/EC and/or local regulatory agency to terminate the study.

7.5. DEVIATION FROM STUDY PROTOCOL

The investigator shall not deviate from study protocol without first obtaining a written approval from the Sponsor, or its official designee, and if applicable, from the local IRB/EC according to local regulations.

In the event of medical emergencies, the investigator shall use appropriate medical judgment and will remove the subject from any immediate hazard, then notify the Sponsor or its official designee and if applicable, the local IRB/EC, within 2 days, of the type of emergency and course of action taken.

Any other changes to or deviations from the protocol will be made as an amendment to the protocol and must be approved by the Sponsor or its official designee and the local IRB/EC

before they can be implemented. Accordingly, the Sponsor will not assume responsibility or liability for any unauthorized deviation from or change to the protocol.

8. INVESTIGATIONAL PRODUCT AND VEHICLE SPECIFICATIONS

8.1. DESCRIPTION OF RZL-012

RZL-012 is an investigational drug administered in a single treatment session via multiple injections into subcutaneous fat.

8.2. FORMULATION, PACKAGING AND LABELING

The RZL-012 drug is a ready to use solution to be injected into subcutaneous fat, supplied in a 1 vial kit. 1 vial contains 250 mg/5 mL RZL-012 in formulation F12.

8.3. STORAGE AND STABILITY OF RZL-012 AND VEHICLE

The RZL-012 kit and vehicle will be stored on site at monitored room temperature conditions $(22 \pm 7 \text{ °C})$ protected from light. Storage space will be separate, designated and adequately labeled as containing investigational product.

Drug product stability has successfully reached 3 years. Site inventory will be managed by the Sponsor according to accumulating stability data. Suitability of the product's expiration date must take into consideration and comply with FIFO (First In First Out) principals.

The storage conditions are summarized in Table 7.

Table 7: RZL-012 Storage Conditions

Storage Conditions	Maximal Storage Duration			
Individual vials:	According to expiration date as will be			
Room temperature (15-30 °C) provided by manufacturer.				
* Drug product stability program has successfully reached 3 years.				

8.4. DOSAGE, DISPENSING AND ADMINISTRATION OF RZL-012 AND VEHICLE

8.4.1. Dosage

RZL-012 therapy is available in vials of 250 mg/5 mL.

The vehicle is available in vials of 5 mL.

8.4.2. Administration and Instructions for Use

Each individual vial must be kept and handled at room temperature.

The vial should be manually shaken before consumption.

1 mL Luer-lock syringes with RZL-012 solution should be filled with 30 G 1/2" sterile needle according to lipoma size (assessed by US), as described below:

Number of Subjects – Active/Placebo	19/19				
Lipoma/Nodule size – diameter (cm)	1-1.9	2-3.9	4-5.9	6-7.9	8-10
Number of Injections - Active/Placebo	2	4	8	10	12

One vial will be used for dosing of one subject. Breached vials will not be re-used for other subjects. Each vial must be placed back into the container. All open vials must be kept until the end of the study for the Sponsor to decide either to discard or return to the Sponsor.

